Protocol

Title: Communication App to Manage Symptoms and Improve Adjuvant Endocrine Therapy Adherence

Protocol date: August 21, 2019

Principal investigator: [name]

NCT Number: NCT03592771

Background

More than 80% of U.S. women with breast cancer have hormone receptor-positive (HR+) tumors (1). They are commonly prescribed adjuvant endocrine therapy (AET) after surgery, chemotherapy and/or radiation (2, 3). Long-term use of AET significantly reduces the risk of hospitalizations, cancer recurrence, and mortality (4, 5). Despite the potential improvement in survival outcomes, evidence suggests that adherence is low (6-12). Multiple studies point to AET-related adverse symptoms as a key reason for non-adherence or premature discontinuation (7, 8, 10, 13-20). In addition to adverse symptoms, other potentially modifiable factors that impact AET adherence include poorer patient-provider communication, fewer perceived treatment benefits, and barriers such as high cost and inconvenience (21).

Patients who do not take the full amount of their AET medication as prescribed or who discontinue their AET treatment early do not receive the full intended treatment benefits and, consequently, are at increased risk for mortality (22-25). Observational studies have found significantly lower adherence (7, 26, 27) to AET among Black women when compared to White women. Racial differences in AET adherence may contribute to mortality disparities between Black and White women with breast cancer (6). This challenge is magnified in Memphis, Tennessee, which has one of the highest mortality disparities in breast cancer survival in the country (28). Survival differences by race persist even after controlling for stage at diagnosis, insurance status, income, and comorbidities (28-30). It is possible that an intervention that standardizes patient-provider communication regarding adherence and symptom management may be able to reduce racial disparities in AET adherence and improve patient health outcomes.

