Medication Adherence Monitoring. The WisePill monitor consists of a pillbox that wirelessly transmits adherence data each time the device is opened. The device uses mobile phone and Internet technologies to provide real-time adherence data. WisePill has been used to track medication adherence for other medications used to treat various diseases (59, 60).

Surveys. Participants are asked to complete brief online surveys every 6 months during their participation in the trial. Participants who do not complete the online follow-up surveys are offered other modalities to improve response rates, including mailing a paper version with a self-addressed return envelope or via phone interview with the research nurse. We will collect the following survey measures as covariates or secondary outcomes: a) a brief three-question, validated instrument to assess health literacy (61); b) the Health Beliefs and Medication Adherence in Breast Cancer (HBMABC) (21) questionnaire, which focuses on patients' perceived susceptibility to breast cancer recurrence and perceived benefits and barriers of AET; c) Self-Efficacy for Managing Symptoms-Short Form instrument (62); d) Communication: Patient and Physician Peer Assessment Module 10-items instrument (63); e) Wheeler et al.'s shared decision-making questions (64); f) sociodemographic characteristics, including education level, relationship status, religious identity, household size, and household income; g) Self-reported medication adherence questions (66); and h) cost, measured via self-reported healthcare utilization (i.e., number of clinic visits, urgent care or emergency visits, hospitalizations, etc). Table 1 describes the key surveys and the relevant time points.

Table 1. Key Survey Measures and Data Collection Timeline

Measure	Description of Measure	Survey Time Points		
		Baseline	12-month Follow-Up	18+ Month Follow-up
Demographics	Age, highest level of education, total household income, race/ethnicity, current relationship status, sexual orientation, gender identity, and religious identity will be collected at baseline	X		
AET medication Adherence	Self-reported medication adherence will be measured with 5 questions about frequency of adherence and main reasons.		X	X
Symptom burden (FACT-ES)	The Functional Assessment of Cancer Therapy Endocrine Symptoms (FACT-ES), a 18-item instrument evaluates endocrine symptoms on a five-point Likert scale [56]	X	X	X

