Quality of life (SF-12)	The Short-Form Health Survey (SF-12), a 12-item instrument that provides summary measures of physical and mental health status will be used [65, 66]	X	X	X

Communication: Patient and Physician Peer Assessment Module; Adapted 1-item measure	The Patient and Physician Peer Assessment Module [61] is an 11-item instrument that assesses patient perceptions of communication with their provider on scale of 1 (poor) to 5 (excellent). Shared decision making will also be assessed using a 1-item question adopted from Wheeler et al. [62]	X	X	X
Self-efficacy for managing symptoms (PROMIS)	The 4-item PROMIS Item Bank v1.0 – Self-Efficacy for Managing Symptoms short form scale will be used to measure confidence in a participant's ability to successfully perform specific tasks or behaviors related to her health in a variety of situations [60]	X	X	X
Healthcare utilization in previous 6-months	A measure developed for this study based on the National Health Institutes Survey (NHIS) [67] will be used to assess healthcare utilization throughout the duration of the study.	X	X	X

Electronic Health Record Chart Abstraction. The following baseline demographic data are abstracted from the patient's electronic health record upon enrollment:

- Date of birth, race/ethnicity, marital status, comorbidities
- Disease stage, tumor histology and grade, hormone receptor and human epidermal growth factor-2 (HER-2) status, menopausal status
- AI therapy and modalities of breast cancer treatment received in the primary adjuvant setting
- Chemotherapy and/or surgery received prior to AET
- Provider Responses to the alerts

Intervention Fidelity Monitoring and Data Management. We adhere to the following quality procedures to ensure treatment fidelity: 1) development of detailed intervention standard operating procedures; 2) electronic monitoring of receipt of emails/texts, app usage, and feedback reports; 3) documentation of all intervention contacts; and 4) weekly meetings to review overall adherence to structured protocols, and problem solving for any issues related to participant challenges. The study coordinator performs weekly data quality checks, and the study statistician performs range checks for data values on a monthly basis. All identifiable data is stored on password protected servers or locked file cabinets that only the study team has access to. The study PI, the study

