Secondary Outcomes and Covariates

Quality of life, patient-provider communication, self-efficacy for managing symptoms, and symptom burden.

Descriptive statistics of baseline characteristics on all participants will be presented and compared among the three treatment groups as means and standard deviations for continuous variables, and as frequencies and percentages for categorical variables, for each stratum, namely, White and Black strata, and for the combined data across strata. One-way analysis of variance (ANOVA) and t-tests for pairwise comparison, or its non-parametric counterparts such as Kruskal-Wallis (or Wilcoxon-Mann-Whitney) test when warranted, and chi-squared or Fisher's exact tests will be used to compare the groups for any differences in characteristics. We will also construct models utilizing the across-strata data to formally test for treatment and race interaction. The primary data analysis will adhere to the intent-to-treat principle.

Healthcare utilization and costs. To ensure completeness, we will combine self-reported healthcare utilization (reported every 6 months) with data abstracted from patient EHRs. Duplicates will be eliminated, and if conflicting information arises, we will assume that the EHR is correct. All utilization will be converted to cost using Medicare reimbursement rates. Using Medicare payment rates is a relatively standard approach in economic analysis because these rates provide a common metric for costing out services across all sectors of care (public or private) (49); this is important because we are actually interested in the underlying resource utilization, not differences in prices. Medicare is also a major payer in all health care markets; almost all payers 'follow Medicare's lead' when determining payment rates. Finally, many Medicare reimbursement rates were originally determined based on cost studies; thus, the Medicare relative fee structure bears some resemblance to the underlying relative cost structure.

For analysis of healthcare utilization data, we will employ two-part Hurdle Poisson models that are appropriate for

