“rate” data (e.g., visits per year). If we find that the data are over-dispersed, we will also explore negative binomial models. These models will yield two sets of coefficients, one related to the probability of any utilization and the other related to the level of utilization conditional on having any utilization. For cost data, we will employ two-part lognormal models to accommodate the high level of skewness. Again, this approach will yield two sets of coefficients: one related to probability of any cost and the other related to level of cost (conditional on having any cost). We have successfully used this approach in previous studies. We will also use survey reports from providers at clinic staff to accurately estimate costs to implement and maintain each intervention. For relative cost-effectiveness, we will calculate 6- and 12-month incremental cost-effectiveness ratios, comparing App or App+Feedback versus usual care at 6 and 12 months.

Missing data. Missing data, especially relating to the primary objective of the study, will be evaluated while the study is ongoing to develop corrective actions if possible. Once the study is completed, the missing data structure will be assessed and appropriate imputation approaches will be implemented if necessary.

Dissemination plans

All objectives of the study, primary and secondary, will be addressed using the final study data and the results will be disseminated via article publications, conference presentations, and local seminars. In addition, a summary of the results will be shared on ClinicalTrials.gov. We do not expect that there will be an open access to the study data from the public.

List of abbreviations

AET: Adjuvant endocrine therapy;

AI: Aromatase inhibitor;

EHR: Electronic health record;

WCCRI: West Cancer Center Research Institute

Declarations

Ethics approval and consent to participate

This study protocol (version 1.17 from August 2, 2019) was approved by the University of Tennessee Health Science Center Institutional Review Board (IRB #: 17-05479-XP IAA). We will obtain written informed consent from all study participants.

Funding

This study is supported by a grant from the National Cancer Institute (1R01CA218155).

References

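### The cost analysis gives no quantity or price source for the endocrine drug whose use the app is meant to raise; if the drug is left out, the cost-effectiveness ratios can favour the app arms

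*Combined protocol and SAP*

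**What the plan says.** The survey list under Data Collection includes, as item (h), "cost, measured via self-reported healthcare utilization (i.e., number of clinic visits, urgent care or emergency visits, hospitalizations, etc". Table 1 describes the instrument as a study-developed measure that "will be used to assess healthcare utilization throughout the duration of the study"; its items are not shown.

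Under Healthcare utilization and costs, "we will combine self-reported healthcare utilization (reported every 6 months) with data abstracted from patient EHRs", and then "All utilization will be converted to cost using Medicare reimbursement rates". The reasons given for Medicare rates concern the pricing of services. Utilization is modelled as a rate, with visits per year as the example, and cost by two-part lognormal models. The only cost named beyond utilization comes from provider and staff surveys, meant to "accurately estimate costs to implement and maintain each intervention". The section ends: "we will calculate 6- and 12-month incremental cost-effectiveness ratios, comparing App or App+Feedback versus usual care at 6 and 12 months". It does not state the effect measure in the denominator.

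On the drug itself, the chart abstraction list, which is collected at enrollment, has "AI therapy and modalities of breast cancer treatment received in the primary adjuvant setting" and mentions no fills. Every participant receives a pill monitor, but the Primary Outcome section confines its data to the adherence comparison. No section says that AET drug cost is included, and none says that it is excluded.

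**The concern.** The app is meant to make women take AET more regularly and for longer. If it works, AET consumption is a direct consequence of assignment and is higher in the app arms. A cost total made up of encounters and program cost would then leave out a cost that rises with the benefit. The incremental cost of App and App+Feedback would be too low in the case where Aim 1 succeeds, and a larger sample would not correct this. At stake is the Aim 3 conclusion, including whether an app arm appears to save money. The adherence comparison is not affected.

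**Working it through.** The plan states no cost figure, so there is none to reproduce. The check has two parts.

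**1. What the described costing contains**

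- Named quantities: clinic visits, urgent or emergency visits, and hospitalizations, followed by an open-ended item.
- Unit prices: Medicare rates, justified for services.
- Added cost: running each intervention.
- AET quantity for costing: none given.
- AET price source: none given.

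Carried out as written, the plan would price encounters and the program, and an analyst would have no instruction for the drug.

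**2. How large an omission could be**

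Inputs from the Power/Sample Size and Primary Outcome sections: adherence of 60% (Usual Care), 75% (App) and 85% (App+Feedback); adherence defined as a proportion of days; a 365-day year. The daily price is not in the documents, so $0.10 to $15 is assumed purely for illustration.

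Reading A takes the percentages as mean proportions of days, with cost following days taken:

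- Extra days = (app-arm adherence − 0.60) × 365
- App: 0.15 × 365 = 54.75
- App+Feedback: 0.25 × 365 = 91.25

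| Assumed price per day | Omitted cost, App | Omitted cost, App+Feedback |
|---|---|---|
| $0.10 | $5 | $9 |
| $1 | $55 | $91 |
| $5 | $274 | $456 |
| $15 | $821 | $1,369 |

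Reading B takes the percentages as shares of adherent women. Extra days = (difference in shares) × (mean proportion of days in adherent women − mean in non-adherent women) × 365. The within-group means are assumed:

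| Assumed means | App | App+Feedback |
|---|---|---|
| 0.90 and 0.60 | 0.15 × 0.30 × 365 = 16.4 | 0.25 × 0.30 × 365 = 27.4 |
| 0.95 and 0.50 | 0.15 × 0.45 × 365 = 24.6 | 0.25 × 0.45 × 365 = 41.1 |
| 0.95 and 0.30 | 0.15 × 0.65 × 365 = 35.6 | 0.25 × 0.65 × 365 = 59.3 |

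Effect on the ratio: suppose its denominator is percentage points of adherence, which the plan does not say. Under Reading A one point is 0.01 × 365 = 3.65 days, so including the drug adds 3.65 × daily price per point: $0.37 at $0.10, $3.65 at $1, and $54.75 at $15.

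Effect on the sign: suppose all other incremental cost for App were −$100 (assumed). At $5 a day, −100 + 273.75 = $173.75, so an apparent saving becomes a net cost. The sign changes at 100 / 54.75 = $1.83 a day.

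With no effect on AET use, the expected distortion is zero.

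**The case against.** A reader might infer that the plan excludes the drug and that its cost results are therefore biased toward the app. The documents do not support either statement. The cost list is open-ended, the Medicare sentence covers all utilization, and the survey items are not shown, so drugs may be intended. The bias also needs a real effect on AET use and spending that follows use. Spending arises on dispensing: a dose missed from a filled bottle saves nothing, whereas stopping refills does. Nor does the Background settle the matter. Its mention of "barriers such as high cost and inconvenience" concerns what affects patients' adherence, not the unit cost of AET in a Medicare-rate analysis. Finally, the costing perspective is unstated, and it bears on whether the drug belongs in the total.

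These points stand, and they make the conclusion conditional. They do not remove it. If drug cost is intended, the plan still has no quantity and no price for it.

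The obvious remedy has its own faults:

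- Pricing only the days on which a dose was taken gives no cost to pills dispensed but not taken. If Usual Care has more of these, the result is biased against the app.
- The abstraction list names AI therapy at baseline but not tamoxifen, although tamoxifen users are eligible. Later medication changes are described as recorded after app alerts, which Usual Care does not generate, so switches could be captured unequally.
- Every participant has a new AET prescription. Adding AET to total cost would make almost every total nonzero and largely empty the first part of the two-part model.

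**Conclusion.** The concern holds conditionally. The costing as described is built on encounters plus program cost and has no quantity or price source for AET. If AET cost is left out and the app increases AET use or persistence, incremental cost in the app arms is understated and both ratios favour the app.

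The direction follows from the trial's own hypothesis. The size cannot be found from the documents. Under Reading A it is about 55 or 91 extra days per woman-year times the price, which runs from trivial to decisive over the assumed prices. It is smaller under Reading B, and smaller where the adherence gain consists of doses otherwise missed from filled bottles. The figures per percentage point are illustrative because the ratio's effect measure is undefined. This is worth correcting before the Aim 3 analysis.

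**What to change.** State in Healthcare utilization and costs that AET drug cost is a component in all three arms, and specify:

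- **Price:** one fixed price list, applied to the prescribed agent (AI or tamoxifen), with the agent and any switch abstracted in the same way and at the same times in every arm.
- **Quantity:** days on therapy to discontinuation, using the persistence measure already defined under Primary Outcome and cut at 6 and 12 months, or fills if they can be obtained. Use WisePill days taken as a sensitivity quantity.
- **Permission:** amend the Primary Outcome sentence that confines the monitor data to the adherence comparison, so that they may also be used for costing. They would still be kept out of the app, the alerts and the feedback.
- **Model:** keep the two-part model for non-AET cost and add AET cost as a separate component.
- **Reporting:** give cost differences and the 6- and 12-month ratios with and without AET cost, and name the ratio's effect measure.

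The cost is some extra chart abstraction, a price list and one more analysis component. The app's cost result may become less favourable. Randomization, the interventions and the primary endpoint are unchanged.

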Our study tests a web-enabled app designed to improve patient-provider communication about AET adherence and related adverse symptoms outside of clinic visits. This builds on the success of our pilot study by: 1) expanding the intervention period from two to six months in order to capture later-onset adverse symptoms that might be slower to develop; 2) following participants for one year, to test longer-term effects of the intervention on medication adherence and other outcomes; and 3) including a larger sample, stratified by race, powered to test the intervention with and without tailored feedback messages.

Methods

THRIVE is a five-year study funded by the National Cancer Institute. During the first year, we completed five focus

groups to refine the study protocol and app (45). In the second year, we launched the randomized controlled trial of a web-based app and tailored messages for women with breast cancer initiating AET. The intervention lasts 6 months, and the primary end point is medication adherence assessed 12-months after enrollment.

Aims of the Study

1. Test if the App and App+Feedback conditions improve AET adherence.
2. Test if the App and App+Feedback conditions improve symptom burden, quality of life, patient-provider communication, and self-efficacy for managing symptoms.
3. Calculate the relative impact of the App and App+Feedback conditions on healthcare utilization and cost.

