The app alerts are based on response thresholds to adherence and symptom questions and are generated to inform the participant's care team (i.e., prescribing physician and nurse) of any concerning responses or trends that emerge from the participant-reported outcomes via the app. WCCRI oncologists guided the alert thresholds, which include: three missed doses within the last week, a 4-point increase in symptom burden on the severity

scale, or a score of 7-10 on the severity scale. Participants are also able to provide a free-text response to report anything they would like at the end of the survey, which is reviewed by the nurse coordinator who determines if a response from the oncology team is required.

These alerts inform providers of potentially concerning symptoms that warrant care team contact with the patient. The alert messages include the event that triggered the alert and are sent to the care team via e-mail. Care teams are asked to respond to alerts within 48 hours. They are able to review concerning responses directly from the patient's EHR to help guide ongoing treatment and make therapeutic adjustments when necessary. AET nonadherence for three days or more within one week prompts a call, even when the cause is not related to an adverse symptom. This facilitates communication between patients and their teams on barriers to AET adherence and provides an opportunity for shared decision-making. A research nurse notes the clinical response and care team contact in the patient's record after each alert (i.e., a phone consult, visit, and any medication changes).

App+Feedback Condition. In addition to the previously outlined procedures, participants randomized to the App+Feedback group will receive weekly tailored feedback messages based on their baseline survey responses and use of the app during the 6-month intervention phase. Some tailored feedback includes links to symptom-specific educational materials and coping strategies for participants who report low-severity symptoms. Using feedback from focus groups, we developed a library of messages with multiple options for each condition in order to prevent desensitization to the same message. Message categories are tailored to participant's responses to the app and baseline survey. Some feedback messages are supplemented with images (see Figure 5).

Data Collection

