months 7-12, participants receive an additional \$120 merchant credit for the second follow-up survey, WisePill battery charge maintenance, and return of the WisePill device. For months 18-36, participants who enroll early are asked to complete follow-up surveys every 6 months and receive \$10 per survey, for a maximum of \$40.

Criteria for modifying allocated interventions

If a participant is discontinued from adjuvant therapy, she is asked to still complete the follow-up surveys, but no longer receives reminder or feedback messages nor completes the app surveys if she was allocated to the app or app+feedback conditions.

Statistical Analysis

Power/Sample Size. Using adherence results from our pilot study and assuming 60% adherence in the 'Usual Care' arm, 75% adherence in the 'App' arm, and 85% adherence in the 'App+Feedback' arm, 95% power to detect a significance adherence difference among the three arms will be achieved with a total of 240 evaluable participants (80 evaluable patients in each arm) with 5% Type-1 error rate. We increase the sample size to 100 for each arm for a total accrual of 300 participants to account for potential 1-year attrition up to 20%. The same sample size would also provide 90% power with 5% Type-1 error rate to significantly detect the Quality of Life difference of 9.3 units where the 'App' and 'App+Feedback' arms are combined against the 'Usual Care' arm with projected standard deviations from the pilot study, of 9.3 and 24.3, respectively.

Primary Outcome

Adherence. Using the electronic pill monitoring system data, adherence will be defined as the proportion of days in which each participant took her medication (as recorded and transmitted via WisePill device opening) according to the prescribed frequency during the 12-month study period. For example, a patient would be considered to be 100% adherent if the pill monitoring electronic data showed that the bottle was opened on 365 days. Days during which patients were hospitalized will be deducted from the denominator. Persistence is commonly defined as the duration from AET initiation to discontinuation of the medication. Persistence will be calculated as the number of days from initiation until the first day of a gap that is 30 days or longer. The electronic medication monitoring

system will be used solely as an outcome measure to compare AET adherence among the study groups, and it will not be used in the app, clinic alerts, or feedback reports.

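### The cost-effectiveness ratios set each app arm against usual care only, so they cannot show what adding feedback to the app costs per unit of effect.

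*Combined protocol and SAP*

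**What the plan says.** The cost-effectiveness plan is one sentence at the end of Healthcare utilization and costs: "we will calculate 6- and 12-month incremental cost-effectiveness ratios", "comparing App or App+Feedback versus usual care at 6 and 12 months". The natural reading is one ratio per app arm at each time point, with usual care as the comparator each time. The sentence names no effect unit. The same section says that provider surveys will be used to "accurately estimate costs to implement and maintain each intervention", so costs will exist for each arm separately.

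The arms are nested. The App+Feedback Condition section states: "In addition to the previously outlined procedures, participants randomized to the App+Feedback group will receive weekly tailored feedback messages". The last paragraph of the Background describes the sample as "powered to test the intervention with and without tailored feedback messages". Aim 3 is: "Calculate the relative impact of the App and App+Feedback conditions on healthcare utilization and cost".

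**The concern.** A clinic has three mutually exclusive options: usual care, the app, or the app with feedback. To choose among them it needs to know what each step up buys. The App+Feedback ratio against usual care averages two steps, from usual care to the app and from the app to the app with feedback. If the second step is poorer value than the first, the average hides it. If the second step is better value than the first, App is a dominated option, and two separate ratios against usual care do not say so unless someone states it.

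At stake is whether the economic results can guide the decision to add feedback. That is a question the three-arm design raises and that its data could answer.

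**Working it through.** The plan states no ratio, cost or precision figure, so there is nothing of its own to reproduce. The check shows when the missing comparison would differ from the planned one.

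**Inputs**
- Effects: 60% (usual care), then "75% adherence in the 'App' arm, and 85% adherence in the 'App+Feedback' arm" (Power/Sample Size). Using these as effects, with adherence points as the unit, is an assumption.
- Effect differences: App minus usual care, 75 − 60 = 15 points; App+Feedback minus usual care, 85 − 60 = 25 points; App+Feedback minus App, 85 − 75 = 10 points.
- Net extra costs over usual care: C1 for App and C2 for App+Feedback. The documents give neither. Both are taken as positive.

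**Formulas**
- Planned ratios: r1 = C1/15 and r2 = C2/25.
- Feedback increment: (C2 − C1)/10 = (25·r2 − 15·r1)/10 = 2.5·r2 − 1.5·r1.
- With k = C2/C1: r2/r1 = (15/25)·k = 0.6·k, and increment/r2 = 2.5 − 1.5/(0.6·k) = 2.5·(1 − 1/k).
- The increment exceeds r2 exactly when r2 > r1, that is, when k > 25/15 = 1.67.

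| k = C2/C1 | Feedback adds, as % of App's extra cost | r2/r1 | Increment ÷ r2 | Status of App |
|---|---|---|---|---|
| below 1.0 | less than 0 | below 0.6 | negative | strictly dominated |
| 1.5 | 50% | 0.9 | 0.83 | extendedly dominated |
| 1.67 | 67% | 1.0 | 1.0 | boundary |
| 2.0 | 100% | 1.2 | 1.25 | not dominated |
| 2.5 | 150% | 1.5 | 1.5 | not dominated |

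Two cases with assumed dollar amounts show the two directions:
- C1 = $100, C2 = $200: r1 = $6.7, r2 = $8.0, increment = $10.0 per point. Adding feedback costs more per point than the planned $8.0 suggests.
- C1 = $100, C2 = $150: r1 = $6.7, r2 = $6.0, increment = $5.0 per point. App is extendedly dominated, and $6.0 against usual care is the right figure for App+Feedback.

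**Precision of the feedback effect, 80 evaluable per arm**
- The Primary Outcome section defines adherence as a proportion of days: "adherence will be defined as the proportion of days in which each participant took her medication". The documents give no SD for it; 15 to 35 points is assumed. SE = SD·√(2/80), which is 2.37 at SD 15 and 5.53 at SD 35. The 95% interval for a 10-point difference (t, 158 df) is 5.3 to 14.7 at SD 15 and −0.9 to 20.9 at SD 35. Power runs from about 99% down to 44%.
- If adherence were instead yes/no, SE = √(0.75·0.25/80 + 0.85·0.15/80) = 0.0627. The interval is −2.3 to 22.3 points and power is about 35%.

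**The case against.** The strongest reply is that nothing planned is wrong. The ratios are labelled as comparisons with usual care, and that is what they are. Aims 1 and 2 ask whether each app condition improves outcomes, which fits a usual-care comparator. Aim 3 concerns utilization and cost, and the Background remark about feedback is about power. A point estimate of the feedback increment could be derived afterwards from the arm-level costs and effects. All of this stands. What remains is that the increment, its uncertainty and a dominance check are not planned.

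It is also fair to say that the unfavourable case is not obviously the likely one. Feedback must add more than 67% of App's whole net extra cost before the planned ratio understates the cost of adding it. On delivery alone, feedback is a set of messages drawn from a prepared library, while the App arm already carries alerts and care-team contact. Net cost also includes healthcare use, however, so the direction is unknown. If an app arm saves money, the ratios can be negative and the table above does not apply.

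A reader might infer three stronger points, and the documents support none of them.
- That Aim 3 is unmet: the planned analyses address it as worded.
- That the unnamed effect unit, the unstated 6-month window and the absent interval method are serious faults in themselves. They are missing detail. Adherence is the sole primary outcome, the WisePill device transmits each opening, so a 6-month window needs no new data, and an analyst would supply an interval.
- That the App ratio is wildly unstable because its effect difference could lie near zero: this rests on a yes/no outcome that the Primary Outcome section does not define, and on holding the cost difference fixed.

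**Conclusion.** The point holds as a minor improvement to a secondary economic analysis. The two planned ratios are valid, but they do not show the value of adding feedback or whether App is dominated, so they cannot support a choice among three nested options. Under the assumptions above (adherence points, the planning rates as effects, positive extra costs), the increment exceeds the planned App+Feedback ratio only when C2 is more than 1.67 times C1; at 2 times it is 1.25 times that ratio. Between 1.0 and 1.67 times App is extendedly dominated, and below 1.0 times strictly dominated. In both of those cases the usual-care comparison for App+Feedback is the right one, and only the statement that App is dominated is lost. The primary adherence analysis is unaffected.

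**What to change.** In Healthcare utilization and costs, keep the two ratios against usual care and add a full incremental analysis:
- Order the three arms by cost, identify any that are dominated or extendedly dominated, say which, and calculate each remaining ratio against the next remaining arm.
- Use adherence over the matching 6- or 12-month window as the effect.
- Report the App+Feedback minus App cost and effect differences with a joint patient-level bootstrap, and apply the same bootstrap to all three pairs of arms.

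The cost is a short paragraph and minor extra analysis, with no new data. The downside is that the feedback increment may be imprecise, so it should be presented as an estimate with its uncertainty.
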